### **Distress Plan**

In addition to the treatment parts listed above, participant distress during assessment and treatment sessions will be actively monitored and addressed by all study personnel (research assistant, interventionist, and the PI). [name] [name] (PI) will train and supervise the research assistant (RA) and the interventionist prior to the initiation of the study. Training will not only include the execution of the protocol but also, handling participant distress and psychiatric emergencies. Training sessions will include role plays and feedback. Once the study is initiated, [name] will meet with the RA and interventionist on a weekly basis to discuss any emergent issues that need to be addressed through further training.

If a participant experiences significant emotional distress during their study (both assessment and treatment visits) they will be referred to an appropriate mental health provider. If they report or present with any severe psychiatric symptoms such as suicidality an emergency protocol will be enacted which includes assessment for hospitalization (See Appendix P: Mental Health Emergency Procedures). [name] is a licensed clinical psychologist in the States of Texas and Rhode Island and has experience in assessing, managing, and supervising staff on procedures for addressing psychiatric emergencies.

## **8.0 Evaluation of Toxicity**

Not applicable.

## **9.0 Criteria for Response**

Not applicable.

## **10.0 Criteria for Removal from the Study**

Subjects who are excluded at the initial screening or withdraw from the study will be given self-help smoking cessation materials and will be referred to alternate smoking cessation programs in the area. Participants may be removed from the study at the PI's discretion for any of the following reasons:

- 1) The participant's behavior disrupts others or prohibits others from receiving and/or benefiting from the treatment.
- 2) The participant begins the use of smokeless tobacco, electronic nicotine

delivery system (ENDS), or other nicotine replacement therapies (NRT) during the course of the study.

- 3) The participant becomes pregnant during the course of the study.

## 11.0 Statistical Considerations

**Proposed Analyses:** In this pilot study, we will summarize descriptive statistics to characterize our study sample and describe between group differences. Descriptive statistics will be tabulated for all study variables which includes demographics, measures of intervention acceptability, feasibility, fidelity, and smoking history, nicotine dependence, and other variables.

We also plan to conduct basic effect size estimates to derive preliminary findings based on pre/post design. With such a small sample size, we will focus on the substantive magnitude of observed between group differences. We will, however report Fischer's exact p-values and the nonparametric Kruskal-Wallis test for equality of rank-ordered population distributions when comparing treatment groups on categorical and continuous outcomes, respectively. Graphical methods will also be used to explore and describe the association between adherence to treatment and smoking in each of the intervention groups.

Aim 3 compares the three treatment groups (CTSC, CTSC+AE, & HE) on the mean percentage of days of NRT adherence during the 12 weeks of treatment. In our preliminary study of Latino smokers (Project Impact) we found that on average participants were adherent on 46.7% (standard deviation=36) of days during the 12 weeks of NRT treatment. Based on this finding, we estimate that our control condition (HE) will show a similar rate of NRT adherence (adherent on 56% of treatment days). We are guided primarily by our expectations that clinically significant improvements in outcomes will be achieved with >75% adherence and we base our estimate of the NRT adherence rate for our CTSC+AE condition on two studies reporting NRT adherence rates for interventions that sought to increase adherence but did not exclusively target adherence. The adherence rates of the experimental condition in these studies ranged from 88-93%. The current study is not only designed to test the feasibility of CTSC and CTSC+AE (Aim 1), but to evaluate the CTSC+AE intervention compared to HE and CTSC groups. It is not expected to be a definitive efficacy trial and the proposed sample will yield power to detect only large effects. We will have power to detect a conservative estimate of 80% adherence in our CTSC+AE condition. When we account for an attrition rate of 20%, a sample of 36 participants can detect a mean difference of 13% or greater between the groups using a 2-tailed alpha = .05. Due to the limited scope of this development project, this study will not be powered for formal hypothesis testing of group differences. Nevertheless, the proposed study will conduct analyses investigating distributional assumptions and co-variation among examined predictors which will inform the design of a future efficacy trial that will be fully powered. Lastly, we will explore potential mediators and moderators (AIM 4) of our primary outcomes and treatments using descriptive statistics, the chi2 test, and correlational analyses

including the bivariate Pearson r. This approach is unable to confirm a significant mediational or moderation effect. It was selected due to our limited sample size. However, our aim is to identify potential trends that can be further tested in a larger and subsequent study using standard mediational and moderation analytic approaches.

**Aim 1:** Evaluate the feasibility, fidelity, and acceptability of the CTSC and CTSC+AE in Latino smokers. Our evaluation of these domains will seek to identify elements of the intervention that are successful or in need of improvement for a planned larger trial. To evaluate these domains we will assess: 1) Recruitment and retention of participants 2) Intervention adherence 3) Program satisfaction 4) The extent to which the intervention was delivered as planned (derived from the Fidelity Checklist [Appendix Z], described in the measures section).

**Aim 2:** To evaluate the preliminary efficacy of the CTSC and CTSC + AE, as compared to HE, on increasing biochemically verified 7-day point prevalence smoking abstinence smoking abstinence rates at 3 and 6 month follow-up in Latino smokers. We hypothesize that participants in the CTSC + AE group will demonstrate significantly greater rates of biochemically verified 7-day smoking point prevalence abstinence at 3 and 6-month follow-up

**Aim 3:** To evaluate the efficacy of the CTSC+AE condition, as compared to the HE and CTSC groups, on increasing adherence to nicotine patch treatment (NRT adherence is defined as the proportion of days of NRT use over the number of patches made available).

**Aim 4 (Exploratory):** To examine potential mediators and moderators of the relationship between our primary outcomes (Aims 1-3) and our treatment groups. For this exploratory aim we will examine several variables that may influence treatment outcomes including gender, age, alcohol use, health related fatalism, sense of control and acculturation.

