## Protocol Body

### 1.0 Objectives

The objective of this study is to conduct a pilot 3-group randomized clinical trial involving three behavioral health interventions for smoking cessation among Latino smokers. Participants will be randomized to one of three interventions: A 1) Health Education (HE) control condition, a 2) Culturally Tailored Smoking Cessation (CTSC) condition or a 3) CTSC + Adherence Enhancement (AE) condition. All three conditions will include three behavioral intervention sessions with a counselor at baseline, 2 weeks and 6 weeks. Participants in all three groups will also receive 12 weeks of Nicotine Replacement Therapy in the form of nicotine patches. We will assess cessation at follow-up which will occur at 3 and 6 month follow up. The specific aims of this project are:

**Aim 1: Evaluate the feasibility, fidelity, and acceptability of the CTSC and CTSC+AE in Latino smokers.** Our evaluation of these domains will seek to identify elements of the intervention that are successful or in need of improvement for a planned larger trial. To evaluate these domains we will assess: 1) Recruitment and retention of participants 2) Intervention adherence 3) Program satisfaction 4) The extent to which the intervention was delivered as planned (derived from the Fidelity Checklist [Appendix Z], described in the measures section).

**Aim 2: To evaluate the preliminary efficacy of the CTSC and CTSC + AE, as compared to HE, on increasing biochemically verified 7-day point prevalence smoking abstinence rates at 3 and 6 month follow-up in Latino smokers.**

**Aim 3: To evaluate the efficacy of the CTSC+AE condition, as compared to the HE and CTSC groups, on increasing adherence to nicotine patch treatment (NRT adherence is defined as the proportion of days of NRT use over the number of patches made available).**

**Aim 4 (Exploratory): To examine potential mediators and moderators of the relationship between our primary outcomes (Aims 1-3) and our treatment groups.** For this exploratory aim we will examine several variables that may influence treatment outcomes including gender, age, alcohol use, health related fatalism, sense of control and acculturation.

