- 3) Our primary research question compares the three treatment groups (CTSC, CTSC+AE, & HE) on the mean percentage of days of NRT adherence during the 12 weeks of treatment. In our preliminary study of Latino smokers (*Project Impact 1*) we found that on average participants were adherent on 46.7% (SD=36) of days during the 12 weeks of NRT treatment. Based on this finding, we estimate that our control condition (HE) will show a similar rate of NRT adherence (adherent on 56% of treatment days). We are guided primarily by our expectations that clinically significant improvements in outcomes will be achieved with >75% adherence and we base our estimate of the NRT adherence rate for our CTSC+AE condition on two studies reporting NRT adherence rates for interventions that sought to increase adherence but did not exclusively target adherence. The adherence rates of the experimental condition in these studies ranged from 88-93%. The current study is not only designed to test the feasibility of CTSC and CTSC+AE (Aim 1), but to evaluate the CTSC+AE intervention compared to HE and CTSC groups. It is not expected to be a definitive efficacy trial and the proposed sample will yield power to detect only large effects. Due to the limited scope of this development project, this study will not be powered for formal hypothesis testing of group differences. Nevertheless, the proposed study will conduct analyses investigating distributional assumptions and co-variation among examined predictors which will inform the design of a future efficacy trial that will be fully powered.
- 4) Other smoked non-tobacco substances can potentially interfere with our carbon monoxide testing. To address this concern, prior to all CO testing, participants will be asked whether they have smoked non-tobacco substances in the last two days. If so, the participant will be asked to provide an additional CO sample after 2 days of non-tobacco substance abstinence.

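### Section 11.0 puts its weight on the size of between-group differences but attaches no between-arm estimate or confidence interval to the contrasts named in Aims 2 and 3

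*Combined protocol and SAP*

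**What the plan says.** All of this is in the combined protocol and SAP.

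- **Focus.** Section 11.0, Proposed Analyses, will "summarize descriptive statistics to characterize our study sample and describe between group differences", and adds that, given the small sample, "we will focus on the substantive magnitude of observed between group differences".
- **Effect sizes.** The one sentence on effect sizes reads "We also plan to conduct basic effect size estimates to derive preliminary findings based on pre/post design". It names no measure.
- **Tests.** The same paragraph promises Fisher exact p-values and the "nonparametric Kruskal-Wallis test for equality of rank-ordered population distributions when comparing treatment groups on categorical and continuous outcomes", respectively. It does not say whether Fisher is applied to all three arms or to pairs.
- **Aim 2 contrasts.** "To evaluate the preliminary efficacy of the CTSC and CTSC + AE, as compared to HE", at 3 and 6 months. Section 11.0 adds "We hypothesize that participants in the CTSC + AE group will demonstrate significantly greater rates" of verified abstinence.
- **Aim 3 contrasts.** "To evaluate the efficacy of the CTSC+AE condition, as compared to the HE and CTSC groups" (Section 1.0, repeated in 11.0). Analytic and Design Considerations, item 3, describes the same question for all arms at once: "Our primary research question compares the three treatment groups".
- **Status of testing.** The Aim 3 paragraph of 11.0 and item 3 both say that the study is not powered for formal tests of group differences and is meant to inform a larger trial.

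**The concern.** The aims pose four pairwise questions, two on abstinence (each at two time points) and two on adherence. The named analysis does not deliver an answer to any of them with its precision.

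For adherence, a Kruskal-Wallis p-value says only that the three distributions are unlikely to be equal. It does not separate CTSC+AE against HE from CTSC+AE against CTSC, and the second of these isolates the adherence add-on. For abstinence, a three-group Fisher p-value would have the same limit, and the text leaves open whether that is what is meant. The Aim 2 hypothesis is directional and concerns one arm, so a three-group p-value cannot address it.

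What is at stake is the use made of the pilot. Its results are to inform the design of a larger trial. Arm summaries plus p-values would let an observed difference of 20 or 30 points pass into that design without any statement of how uncertain it is. They also leave the effect measure to be chosen after the data are seen.

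**Working it through.** **Inputs from the documents**
- 36 participants, 12 per arm (Section 4.0).
- Adherence SD 36, mean 46.7%, from the preliminary study (Section 11.0, Aim 3 paragraph and item 3).
- Expected adherence: HE 56%, CTSC+AE 80% (Aim 3 paragraph). Difference 80 - 56 = 24 points.
- Missing days count as non-adherent or smoking (Analytic and Design Considerations, item 6), so all 12 per arm stay in the analysis.

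**Assumed, because the documents do not give them:** the SD in the CTSC+AE arm, the CTSC mean, and all abstinence counts and rates.

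**The plan's own between-group figure.** The power statement says that 13 points can be detected. With SD 36 and 12 per arm, SE = 36 × √(2/12) = 14.70. Two-sided power for 13 points is Φ(13/14.70 - 1.96) = Φ(-1.08), about 14%. The figure does not reproduce. That is a separate matter: it is a planning number, not a reported estimate, and nothing below depends on it.

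**Adherence, pairwise 95% interval.** Half-width = t(.975, df) × √(SD₁²/12 + SD₂²/12), with Welch degrees of freedom.

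| SD HE / CTSC+AE | SE | df | t | Half-width | 24-point difference |
|---|---|---|---|---|---|
| 36 / 36 | 14.70 | 22.0 | 2.074 | 30.5 | -6.5 to +54.5 |
| 36 / 30 (assumed) | 13.53 | 21.3 | 2.078 | 28.1 | -4.1 to +52.1 |
| 36 / 20 (assumed) | 11.89 | 17.2 | 2.108 | 25.1 | -1.1 to +49.1 |
| 25 / 25 (assumed) | 10.21 | 22.0 | 2.074 | 21.2 | +2.8 to +45.2 |

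If HE behaved like the preliminary study, the difference would be 80 - 46.7 = 33.3 points and the interval at SD 36 would be +2.8 to +63.8. If dropouts were left out instead of counted as non-adherent, the half-width at SD 36 would be 33.8 with 10 per arm and 36.0 with 9 per arm.

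**What the omnibus test can separate.** In a simulation with 12 per arm (normal data, SD 36, 10,000 runs), Kruskal-Wallis rejected in about 32% of trials when the HE/CTSC/CTSC+AE means were 56/56/80 and in about 32% when they were 56/80/80. In the first case the add-on does all the work. In the second it does none. The test reacts alike to both.

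**Abstinence, illustration with assumed counts.** Newcombe score interval for a risk difference, built from the two Wilson intervals, 12 per arm:
- 4/12 against 1/12: +25.0 points (-8.4 to +53.4), Fisher p = .32.
- 6/12 against 1/12: +41.7 points (+5.1 to +67.2), pairwise Fisher p = .069. If CTSC also had 1/12, the three-group Fisher p would be .027.

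The last pair shows that the unstated form of Fisher can matter. It is one chosen table. Computed exactly over assumed true rates (HE/CTSC/CTSC+AE), the three-group test and the pairwise test of CTSC+AE against HE fall on opposite sides of .05 in 0.9% of trials at 10/10/10%, 2.2% at 20/20/20%, 5.1% at 10/20/30%, 8.7% at 10/10/30% and 18% at 10/10/50%.

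**The case against.** The strongest reply is that this is a 36-person pilot that says openly it is not a formal test. Descriptive statistics are to be tabulated for all variables, so the arm means, SDs and counts would show direction, and any reader could compute an unadjusted interval from them. The comparators are written into 11.0, and scales are hinted at: mean percentage of days, abstinence rates, a mean difference in the power statement. All of that is true, and it limits the harm. It does not remove it. The mean difference appears only as a power figure, no output is tied to the comparators, and a plan that disclaims testing yet names only p-values as inference has its emphasis the wrong way round.

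Four stronger readings are tempting, and the documents do not support them.
- *The plan never says which arms are compared.* It does, in the aims restated in 11.0. What is missing is the estimate and its interval.
- *The ambiguity about Fisher would often decide the result.* The exact frequencies above are below 10% unless the assumed effect is very large, and crossing .05 counts for less in a plan that disclaims formal tests.
- *The pre/post effect sizes invalidate Aims 2 and 3.* Everyone smokes at entry and current NRT users are excluded, so change from baseline adds nothing to the follow-up value. That makes it uninformative for these outcomes but harmless, and the next sentence turns to between-group magnitude.
- *Leaving gender, the stratification factor, out of the comparisons is a material flaw.* At SD 36, adjustment would take the half-width from 30.5 to 30.6 if gender explains nothing, or to 29.0 if it explains 10% of the variance. Cells would hold about 6 people at best, and the named tests do not adjust for it.

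**Conclusion.** The point holds as a mismatch between the stated focus and the named analysis. Section 11.0 promises magnitude and names the comparators, but plans no between-arm estimate or interval for them. Its only inferential outputs are an omnibus test and Fisher p-values of unstated form.

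The size is best seen in adherence. The plan's expected 24-point difference would carry an interval about 61 points wide (2 × 30.5) at the documents' SD. The interval includes zero at that SD, and still does if the CTSC+AE SD is as low as 20. It excludes zero only under more favourable assumptions, such as both SDs at 25 or HE at 46.7%. This rests on 12 analysed per arm, SD 36 in HE and a t-based interval. The abstinence figures rest on assumed counts and serve only as illustration.

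A reader might infer that the trial's comparisons are invalid. They are not: randomised arms would be summarised and tested. The defect is that what the pilot can and cannot say about each named contrast would go unreported.

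**What to change.** In section 11.0:
1. **Aim 2.** Report the risk differences CTSC against HE and CTSC+AE against HE, with score-type 95% intervals, at 3 and at 6 months.
2. **Aim 3.** Report the mean differences in adherence CTSC+AE against HE and CTSC+AE against CTSC, with 95% intervals, on one stated denominator. Sections 1.0 and 7.0 and the restated aims divide by patches made available. The Aim 3 paragraph of 11.0 and item 3 use days in the 12 weeks. Because spare patches are dispensed (Sections 6.0 and 14.0), the two need not agree.
3. **Labelling.** These are six intervals (2 contrasts × 2 time points, plus 2). Call them exploratory and unadjusted for multiplicity.
4. **P-values.** Keep Kruskal-Wallis and Fisher as secondary, and state that Fisher is pairwise for the named contrasts. A three-group version may be added.

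The cost is a few sentences and slightly more analysis, with no new data or participants. The downside is that wide intervals will make the results look less favourable than bare arm summaries would.

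### The 56% control-arm adherence rate is not reconciled with the 46.7% it is said to rest on, and the Aim 3 claims of power for 80% adherence and for a 13% difference fail on the plan's own inputs

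*Combined protocol and SAP*

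**What the plan says.** The Aim 3 paragraph of Section 11.0 reports from the preliminary study that "on average participants were adherent on 46.7% (standard deviation=36) of days during the 12 weeks of NRT treatment". It presents the next figure as resting on that finding: "we estimate that our control condition (HE) will show a similar rate of NRT adherence (adherent on 56% of treatment days". Item 3 of Analytic and Design Considerations repeats both figures ("on average participants were adherent on 46.7% (SD=36) of days during the 12 weeks of NRT treatment") and gives this comparison its standing: "Our primary research question compares the three treatment groups (CTSC, CTSC+AE, & HE) on the mean percentage of days of NRT adherence".

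The adherence subsection of Section 2.0 gives another figure, 56.6% over a 12-week patch regimen, from the team's prior work. It does not name the study or the adherence measure.

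The Aim 3 paragraph, but not item 3, then makes two claims about power. The first is "We will have power to detect a conservative estimate of 80% adherence in our CTSC+AE condition". The second, after allowing for 20% attrition, is that "a sample of 36 participants can detect a mean difference of 13% or greater between the groups using a 2-tailed alpha = .05". The same paragraph says that the sample suits only large effects and that "this study will not be powered for formal hypothesis testing of group differences". For continuous outcomes the Proposed Analyses text names "the nonparametric Kruskal-Wallis test for equality of rank-ordered population distributions".

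**The concern.** There are two linked problems.

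First, 56% does not follow from 46.7%, and the plan gives no adjustment that would lead from one to the other. Either a different source was used and not cited, or one of the figures is out of date. The documents do not settle which.

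Second, the paragraph makes claims that cannot all stand. It says that 80% adherence and a 13% difference can be detected, that only large effects can be detected, and that the study is not powered for group comparisons. With an SD of 36, 13 points is a standardised difference of 13/36 = 0.36, which is not large.

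This is the comparison that the plan calls its primary question, and the results are meant to inform a fully powered trial. A reader who believes the power sentences could take a non-significant Aim 3 result as evidence against CTSC+AE. A team that reuses 56% or 13 points could mis-size the next study.

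**Working it through.** **Inputs from the plan**
- Preliminary rate 46.7%, SD 36; HE planning rate 56%; CTSC+AE rate 80% (Section 11.0).
- 36 participants, 12 per arm (Section 4.0).
- Attrition 20% and two-sided alpha 0.05 (Section 11.0).
- Missing days counted as non-adherent under intent-to-treat (Analytic and Design Considerations, item 6).

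**Derived inputs**
- Unexplained step: 56 − 46.7 = 9.3 points.
- Implied differences: 80 − 56 = 24 points; 80 − 46.7 = 33.3 points.
- Evaluable per arm: 36 × 0.8 / 3 = 9.6. If the missing-data rule keeps everyone who drops out in the analysis, it is 12. The 12-per-arm rows below are favourable, because they keep the full difference even though dropouts' missing days would count as zero.

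**Assumptions**
- The plan gives no SD for CTSC+AE. I use 36, and also a smaller value that allows for the 0–100% scale. The largest possible SD at mean m is √(m(100 − m)). At 46.7% the observed SD is 36/√(46.7 × 53.3) = 0.722 of that maximum. The same fraction at 80% gives 0.722 × √(80 × 20) = 28.9. This is a heuristic.
- The 13% is read as percentage points. As a relative change from 56% it would be only 0.13 × 56 = 7.3 points, with less power still.
- 80% power is an assumed benchmark.

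**Trying to reproduce 13%.** By normal approximation, the difference detectable with 80% power is (1.96 + 0.84) × 36 × √(2/n). This gives 46.0 points at n = 9.6 and 41.2 at n = 12. Wrongly using the whole sample of 36 as the size of each arm still gives 23.8, and a one-sample calculation with 36 gives 16.8. None gives 13. On the t-test, 80% power at 13 points and 9.6 per arm needs a common SD of about 9.6 points, against the stated 36.

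**Power of a two-sample t-test, HE against CTSC+AE.** SE = √((SD₁² + SD₂²)/n), noncentrality = difference/SE, df = 2n − 2. For example, at n = 9.6 with SD 36 in both arms, SE = √(2 × 1296/9.6) = 16.4, and 24/16.4 = 1.46.

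| n per arm | SD HE / CTSC+AE | SE | 24 points (from 56%) | 33.3 points (from 46.7%) | 13 points |
|---|---|---|---|---|---|
| 9.6 | 36 / 36 | 16.4 | 28% | 48% | 12% |
| 9.6 | 36 / 28.9 | 14.9 | 33% | 56% | 13% |
| 12 | 36 / 36 | 14.7 | 35% | 58% | 13% |
| 12 | 36 / 28.9 | 13.3 | 41% | 67% | 15% |

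One result in the first row does not depend on the 80% benchmark. An observed difference must exceed 2.108 × 16.43 = 34.6 points to reach p < 0.05, so either implied difference, observed exactly, would be non-significant.

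**The planned test.** Simulated three-group Kruskal-Wallis tests were run with assumed beta-shaped adherence and CTSC+AE SD 36 or 28.9. In one set of runs CTSC was placed level with HE or halfway to 80%. With 9 or 10 per arm, power was 27–52% from 56% and 44–64% from 46.7%. With 12 per arm and similar shapes it was about 34–60% and 60–74%. These figures depend on the assumed shapes, but they lead to the same conclusion.

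**The case against.** The strongest defence is that this is a pilot. The plan says that it is not definitive, stresses the size of observed differences over tests, and disclaims power for formal hypothesis testing. N = 36 is not derived from 56%, and 56% is the more cautious of the two rates because it narrows the gap to 80%. All of that stands and limits the weight of the point. It does not rescue two sentences that assert a property the design lacks.

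The 56.6% in Section 2.0 also weakens any claim that 56% has no basis. The fair description is two prior-work figures that have not been reconciled. A reader might infer a slip of arithmetic, or a rate chosen to flatter the design. The documents show no calculation from 46.7% to 56%, and the lower rate would have given the more favourable power.

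Single power figures would be too precise. The lowest values (28% and 48%) need 9.6 per arm and an SD of 36 at a mean of 80%, where the maximum is 40. Ranges are the right form.

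Pooling HE and CTSC as comparators helps the plan. By normal approximation with 12 against 24 and SD 36, power is 47% from 56% and 74% from 46.7%. Adding the smaller CTSC+AE SD gives SE = √(28.9²/12 + 36²/24) = 11.1, and about 58% and 85%. So 80% can be passed only by stacking favourable assumptions, including equal means in HE and CTSC, and only from 46.7%, which is not the rate the plan adopts.

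**Conclusion.** The point holds, at minor to moderate weight. The HE planning rate is not reconciled with its stated source. For HE against CTSC+AE, the claim about 80% adherence has about 28–41% power from 56% and 48–67% from 46.7%. The 13-point claim has 12–15%. These ranges rest on a t-test, an HE SD of 36, a CTSC+AE SD of 36 or about 29, and 9.6 to 12 per arm.

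Two stronger inferences should not be drawn. One is that the trial must be enlarged: the sample size is not built on these figures, and the plan disclaims formal testing. The other is that the true detectable difference is about 49 points, the t-test value for 80% power at 9.6 per arm with SD 36. From 56% it would mean 56 + 49 = 105% adherence. From 46.7% it would mean 95.7%, where the SD cannot exceed √(95.7 × 4.3) = 20.3, so an SD of 36 is impossible.

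**What to change.** 1. Check the preliminary data. State one HE planning rate, with its source and its own SD, in both the Aim 3 paragraph and item 3 of Analytic and Design Considerations. If 56% is kept, say why it differs from 46.7%. Align the 56.6% in Section 2.0 only if it reports the same study.
2. Preferably delete the 80%-adherence power sentence and the 13% sentence. The statements that only large effects are detectable and that the study is not powered for formal testing can then stand without contradiction.
3. If a power statement is wanted, give a range for the chosen difference and name the SD in each arm, the test and the number per arm. Say whether that number is 9.6 or 12, consistently with the missing-data rule in item 6.
4. Do not insert a 49-point detectable difference.

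The cost is a look at existing data and a few sentences of text. The stated power becomes less favourable. The sample size of 36, the visits, the endpoint and the analyses do not change.

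### With the plan's own SD of 36 and 12 per arm, the trial cannot detect a 13-point adherence difference and is not powered for 80% adherence

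*Combined protocol and SAP*

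**What the plan says.** Section 4.0 sets 36 participants, 12 per condition. Section 11.0, Analytic and Design Considerations, item 3, calls the three-group comparison of mean percentage of adherent days the primary research question. It reports from the preliminary study that "on average participants were adherent on 46.7% (SD=36) of days during the 12 weeks of NRT treatment". From this, "we estimate that our control condition (HE) will show a similar rate of NRT adherence (adherent on 56% of treatment days".

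The Aim 3 paragraph of Section 11.0 then makes two numerical claims: "We will have power to detect a conservative estimate of 80% adherence in our CTSC+AE condition", and, after 20% attrition, "a sample of 36 participants can detect a mean difference of 13% or greater between the groups using a 2-tailed alpha = .05". It names no power level, no test for the calculation and no other SD. In the same paragraph, "the proposed sample will yield power to detect only large effects" and "this study will not be powered for formal hypothesis testing of group differences".

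Under Proposed Analyses, "we will focus on the substantive magnitude of observed between group differences"; continuous outcomes are compared by the "nonparametric Kruskal-Wallis test for equality of rank-ordered population distributions". Item 6 of the design considerations scores days without data as non-adherent. The adherence subsection of Section 2.0 gives 56.6% as the adherence seen in prior work.

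**The concern.** Thirteen points is 13/36 = 0.36 SD. Twelve people per arm cannot reliably detect a difference of that size, and it does not fit a statement that only large effects are detectable. The claim about 80% adherence implies a difference of 24 points (80 − 56), or 0.67 SD, which is also ambitious for arms of 12.

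The 13% sentence is the only numerical detectable-difference statement for the primary research question. A reader who takes it at face value, including whoever designs the planned larger trial, will think the pilot is more than three times as sensitive as it is. Because the analysis is meant to dwell on the size of group differences, the width of the confidence interval is the figure readers need, and the plan does not give it.

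**Working it through.** **Inputs.** SD 36, two-tailed alpha .05 and 20% attrition (Section 11.0, Aim 3 paragraph); 12 per arm (Section 4.0). Control mean 56% (assumed in the plan) or 46.7% (preliminary study); CTSC+AE mean 80%. The planned difference is 80 − 56 = 24 points, or 80 − 46.7 = 33.3 points. Attrition taken as loss leaves 12 × 0.8 = 9.6 per arm. Scoring missing days as non-adherent would keep 12, so both sizes are shown. Power levels of 50, 80 and 90% are assumptions.

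**Trying to reproduce 13.** Two-arm comparisons, one- and two-sided tests, CTSC+AE against the other two arms pooled, three-group ANOVA, 18 v 18, and even 36 per arm were tried. No between-group version gives 13 points at 50% power or more. One formula does give the number: 1.96 × 36/√28.8 = 13.1, the 95% margin for a single mean in all 36 less 20%. That this is its origin is conjecture, and it is not a difference between groups.

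**Precision.** SE = SD × √(2/n); half-width = t × SE.
- n = 12: 36 × √(2/12) = 14.70; 2.074 × 14.70 = 30.5 points.
- n = 9.6: 36 × √(2/9.6) = 16.43; 2.108 × 16.43 = 34.6 points.

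**Power and detectable difference.** Two-arm t-test, noncentral t with noncentrality difference/SE, SD 36 in both arms:

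| | 12 per arm | 9.6 per arm |
|---|---|---|
| Power for 13 points | 13.5% | 11.6% |
| Power for 24 points | 34.6% | 28.1% |
| Power for 33.3 points | 58.2% | 48.1% |
| Detectable at 50% power | 30.1 | 34.1 |
| Detectable at 80% power | 43.1 | 48.8 |
| Detectable at 90% power | 49.9 | 56.5 |

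As a hand check at 80% power with 12 per arm, the normal approximation gives (1.960 + 0.842) × 14.70 = 41.2 points.

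**What the claims would need.** For 80% power with SD 36, 13 points needs 122 per arm, 24 points needs 37 and 33.3 points needs 20. With the planned sample, the SD would have to be about 10 to 11 for 13 points, 18 to 20 for 24 points, or 25 to 28 for 33.3 points. If the SD were 20 to 30 (an assumption), the detectable difference with 12 per arm would be 24 to 36 points.

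**CTSC+AE against HE and CTSC pooled (12 v 24; 9.6 v 19.2).** Power is 17% and 14% for 13 points, 45% and 37% for 24 points, and 72% and 62% for 33.3 points.

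**The planned Kruskal-Wallis test.** Its power depends on distribution shapes and a CTSC+AE SD that the documents do not give. Simulation used 8,000 trials per scenario, 12 per arm, beta or normal shapes, SD 36 in HE and CTSC, and CTSC+AE SD from 20 to 36:
- Means 56/56/80 (HE/CTSC/CTSC+AE): 30 to 59%.
- Means 56/68/80: 21 to 51%.
- Means 56/56/69 (a 13-point difference): 9 to 17%.
- Means 46.7/46.7/80, the most favourable case: 57 to 78%.

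**The case against.** The 13% figure has no defence on any between-group reading. The best counter-case concerns the 80% adherence claim.

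Aim 3 compares CTSC+AE with the other two groups, so a pooled contrast is a fair reading. The SD of 36 comes from a sample averaging 46.7%, and the plan never says it applies to an arm averaging 80%. On a 0–100 scale with mean 80, the largest possible SD is 40, so 36 there implies an almost two-point distribution. With beta-shaped data, a control mean of 46.7%, no attrition and 12 v 24 pooled, simulated Welch-test power is 92, 84, 76 and 69% for CTSC+AE SDs of 20, 25, 30 and 36. Mann-Whitney power is 75 to 83%. So 80% power is reachable, but only with a smaller assumed SD, a control rate other than the plan's 56%, no attrition and a test other than the one planned. At 56%, the same pooled simulations give 38 to 71%.

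The consequence is also modest, and this point stands. The plan disclaims powering for formal tests and concentrates on description, it does not derive 36 participants from the 13% figure, and item 3 of the design considerations repeats the rationale without either power claim.

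A further fair caution is that ±30 points may be a best case. If 20% of each arm gave no data and were scored zero (an assumption), means of 56 and 80 become 44.8 and 64.0. The SDs then rise to about 39 in HE and 39 to 45 in CTSC+AE (starting from SDs of 25 to 36), and the half-width becomes about 33 to 36 points.

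**Conclusion.** The concern holds. The 13% statement is wrong as written: the difference detectable at 80% power is 43 to 49 points, more than three times the stated figure. The claim of power for 80% adherence is also unsupported. With SD 36 it reaches 28 to 35% in a two-arm comparison and 37 to 45% pooled against the stated 56%, and at most 72% pooled against 46.7%. These results rest on SD 36 in every arm, two-sided .05, and 12 or 9.6 per arm. The plan's disclaimers contradict the two figures and do not make them true. The point should be fixed, but the pilot purpose limits its consequence.

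A secondary point is the control rate. A rate of 56% is called similar to a finding of 46.7%, a gap of 9.3 points, while Section 2.0 reports 56.6%. The documents do not show whether 46.7% and 56.6% come from the same study. The choice moves the planned difference between 24 and 33.3 points but rescues neither claim.

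**What to change.** In the Aim 3 paragraph of Section 11.0, delete the 13% sentence and the claim of power for 80% adherence. Replace them with a precision statement such as:

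> With 12 per arm and SD 36, the 95% CI for a difference between two arms is about ±30 points. As a guide, a two-arm t-test at two-sided .05 has 80% power for about 43 points (about 49 if 20% are lost and only completers are analysed).

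State how the 20% attrition enters, given that item 6 scores missing days as non-adherent, and whether the SD of 36 already reflects such scoring. If not, say that ±30 is a lower bound. If power is quoted for the Kruskal-Wallis test, give a range with its distributional assumptions.

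Separately, reconcile 46.7%, 56% and 56.6% across Sections 2.0 and 11.0, or cite the source of the 56%, and restate the planned difference to match.

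The cost is wording only. Enrolment, endpoint and analysis are unchanged, and the stated figure becomes less favourable.
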